The nutritional enhancement of fermented foods is largely due to the enzymatic breakdown of complex macronutrients—carbohydrates, proteins, and lipids—into more digestible forms such as simple sugars, fatty acids, and amino acids. However, fermentation can also produce resistant proteins, which are poorly soluble in water and may influence food matrix viscosity, similar to dietary fibers (16). Additionally, the fermentation of amino acids by these microbes can lead to the production of short-chain fatty acids (SCFAs), which are associated with improved glucose tolerance through reduced hepatic glucose output and lower circulating free fatty acid levels (6,9,17–19). Furthermore, intervention studies involving lactic acid bacteria (LAB) fermented foods such as kimchi have demonstrated reductions in health parameters such as body weight, body fat, waist circumference, fasting blood glucose levels, C-reactive protein levels (CRP), and blood pressure compared to their unfermented counterparts (16,20,21). These findings suggest that fermentation may play a pivotal role in enhancing the nutritional and functional properties of plant-based protein sources.

In this context, the fermentation of legumes may support the dietary transition from animal-based to plant-based proteins by improving the nutritional quality of legume-derived proteins. Fermented foods are deeply rooted in traditional diets worldwide, with legumes such as soybeans, black gram, chickpeas, and mung beans commonly used in fermentation practices (22–24).

This study focuses on locally grown Danish legumes - including fava beans, peas, and lentils **to explore the potential of LAB fermentation in enhancing their nutritional and functional properties.** While the health benefits of legumes and LAB-fermented fruits and vegetables are well-documented, the specific effects of LAB-fermented legumes remain a relatively novel area within food science.

It is hypothesized that a daily intake of 100 grams of LAB-fermented or unfermented legumes will lower the levels of blood glucose, inflammation, and cholesterol, change gut microbiome composition, and increase SCFAs in adults, compared to a control period consuming a habitual diet. Furthermore, it is hypothesized that fermented legumes have additional health effects in terms of changes in body composition compared to unfermented legumes.

3. Methods

Study design

A parallel two-armed randomized trial.

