The participants are randomly assigned to two experimental groups based on a randomized trial design: two weeks of habitual dietary intake (control period), two weeks of LAB fermented foods, or two weeks of unfermented foods.

The control period is from zero to 14 days, and after these two weeks, baseline data will be collected from all subjects. The second intervention period lasts from day 14 to day 28 (Fig. 1), during which participants will be instructed to consume 100 g of either fermented or unfermented legumes every day, seven days a week, for two weeks.

[figure not shown]

Fig. 1: Trial design

Study population

Healthy adults are recruited from the University College Absalon or the University of Copenhagen canteens from two locations: University College Absalon in Slagelse, Denmark, and University of Copenhagen in Frederiksberg, Denmark.

Inclusion criteria:

- Adults, 18 – 60 years.
- No diabetes.
- Biological sex includes both males and females.

Exclusion criteria:

- Treatment with antibiotics within the last three months.
- Ongoing treatment with non-steroidal anti-inflammatory drugs.
- Metabolic diseases, including diabetes.
- Inflammatory bowel disease (IBD), such as Crohn's disease or ulcerative colitis.
- Allergies or intolerance to legumes.
- People that report eating > 25 g per day of legumes as part of their habitual diet.

Sample size calculation:

Initially, the power calculation is performed by a parallel two-armed comparison of the change in continuous blood glucose levels from baseline (control period). A total of **50 participants (25 participants in each group)** should be recruited to be able to detect a clinically relevant difference of approximately 9 mg/dL in fasting blood glucose (American Dietetic Association (ADA) 2024) between the groups adjusted (fermented vs. unfermented legumes) (18,23–25), assuming a standard deviation of approximately 10-11 mg/dl, a power of 0.8, and a significance level of 0.05, and includes a 10% dropout adjustment. There will be a running inclusion from September 2026.

Control period

All participants are instructed to adhere to their habitual diet during the 14-day control period.

Intervention period

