Waist and hip circumference (Waist/hip ratio), cm	Waist circumference was measured at the midpoint between the lowest rib and the upper part of the iliac bone in a standing position. Hip circumference was measured at the site of the largest circumference between the waist and thighs.	x	x	x
Gut microbiome and metabolites				
Gut microbiome composition	Near-full length 16S rRNA gene amplicon sequencing	x	x	x
Short chain fatty acids (SCFA) and other metabolites	¹ H NMR spectroscopy	x	x	x
Other variables				
Dietary intake	Three days' dietary records with photos	x		x
Digestive abnormalities	IBS Severity Scoring System questionnaire	x	x	x

4. Statistical analysis

Stages of data processing will begin with descriptive analyses of variables secondary to outcomes for all participants at baseline. These characteristics will be tested using analysis of covariance (ANCOVA) when the data are normally distributed, and the Mann–Whitney U test when the data are not normally distributed. Comparisons of the incremental area under the curve (AUC) in the control (baseline) period will be performed against the two groups (group 1 and group 2), and differences between groups will also be assessed.

Continuous variables will be presented as the mean and 95% confidence interval (CI) in the format [lower limit, upper limit] when the data are normally distributed. Differences between continuous variables will be tested using ANCOVA. Categorical variables will be presented as percentages (e.g., sex), and differences will be tested using Fisher's exact test to compare groups (group 1 and group 2). A P-value < 0.05 will be considered statistically significant. Statistical analyses will be conducted using a statistical software program for scientific research, such as R (RStudio; © 2009–2023 Posit Software, PBC).

For 16S rRNA gene amplicon sequencing data, raw FASTQ data will be subjected to second-level demultiplexing, quality filtering, and amplicon sequence variant (ASV) definition, as well as taxonomy assignment, using the in-house established LACA pipeline (<https://github.com/yanhui09/laca>). Subsequently, the effects of the intervention on alpha- and beta-diversity metrics, compositional changes, and correlations with anthropometrics, metabolites, and intervention arm will be evaluated as previously described (34,36).

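### Section 4 gives only ANCOVA for differences in continuous variables, which does not fit the within-participant comparison of legumes with the control period

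*Protocol*

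**What the plan says.** The design (protocol section 3) has two consecutive 14-day periods. In the first, "All participants are instructed to adhere to their habitual diet during the 14-day control period". Then "The second intervention period lasts from day 14 to day 28", when each participant eats either fermented or unfermented legumes. Nobody serves only as a control.

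The first hypothesis (section 2) is that either legume diet lowers glucose, inflammation and cholesterol, changes the microbiome and raises short-chain fatty acids "compared to a control period consuming a habitual diet". Fermented against unfermented is the second hypothesis.

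Section 4 plans the matching analysis for glucose: "Comparisons of the incremental area under the curve (AUC) in the control (baseline) period will be performed against the two groups". It adds that differences between the groups will also be assessed. That sentence attaches no test. The general rule for continuous data follows: "Differences between continuous variables will be tested using ANCOVA". The same treatment is later extended to each fecal metabolite.

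Two other tests are named, with narrower scope. For baseline characteristics the section gives "the Mann–Whitney U test when the data are not normally distributed". For categorical variables it gives Fisher's exact test between group 1 and group 2. No paired test, signed-rank test, repeated-measures or mixed model, participant effect or ANCOVA covariate is mentioned.

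**The concern.** The control-period value and the intervention value in an arm come from the same people and will normally be positively correlated. A comparison of the two has to use that correlation. The only stated rule that reaches the comparison is ANCOVA, and neither of its usual forms serves:

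- With the control period as a group beside the two legume groups, each participant enters twice as if two people had been measured. The rows for the control period also have no baseline covariate, because the control value is the outcome there.
- With the control-period value as covariate, the arm coefficient estimates fermented minus unfermented. Legume against control is not what it tests.

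So the first hypothesis would get either a test with over-wide intervals or no explicit test. A real fall from the control period could be reported as no effect, although each participant is available as his or her own control.

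**Working it through.** **Inputs from the protocol** (section 3, sample size calculation): 50 participants, 25 per group; difference 9 mg/dL; SD about 10-11 mg/dL (midpoint 10.5 used here); power 0.80; significance level 0.05 (two-sided assumed); 10% dropout. **Assumed:** the within-person correlation r between periods, which the protocol does not give (range 0.3 to 0.9), and equal SD in the two periods.

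**1. The plan's own figure.** n per arm = 2 × (1.960 + 0.842)² × 10.5² / 9² = 21.4, rounded up to 22. With dropout, 22 / 0.9 = 24.4, rounded up to 25, so 50 in total. The stated figure is reproduced at the midpoint SD (SD 10 gives 46 and SD 11 gives 54). It is sized on fermented against unfermented, which is a between-arm contrast.

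**2. Standard error of control against intervention in one arm.**

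- Treated as independent: SD × sqrt(2/n)
- Correct, paired: SD × sqrt(2(1 - r)/n)
- Ratio: 1/sqrt(1 - r), whatever the SD and n

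With n = 22 completers and SD 10.5, the independent value is 10.5 × sqrt(2/22) = 3.17 mg/dL.

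| r (assumed) | Paired SE, mg/dL | Ratio |
|---|---|---|
| 0.3 | 2.65 | 1.20 |
| 0.5 | 2.24 | 1.41 |
| 0.7 | 1.73 | 1.83 |
| 0.9 | 1.00 | 3.16 |

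The mg/dL values are only a scale for illustration, since the announced comparison is of incremental AUC. The ratios carry over.

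**3. Control values of both arms pooled (50) against one arm (25), in SD units.** Treated as independent: sqrt(1/50 + 1/25) = 0.245. Correct: sqrt(1/25 + 1/50 - 2r/50) = 0.200, 0.179 and 0.155 for r = 0.5, 0.7 and 0.9. The ratios are 1.22, 1.37 and 1.58, smaller than for a single arm.

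**4. Effect on the test.** Simulation with n = 22 and a nominal two-sided 0.05 (20,000 runs for the t-tests). The illustrative true fall of 5 mg/dL is assumed.

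| r | Type I error, independent | Type I error, paired | Power, independent | Power, paired |
|---|---|---|---|---|
| 0.5 | 0.007 | 0.052 | 0.29 | 0.56 |
| 0.7 | 0.001 | 0.047 | 0.25 | 0.79 |

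The error goes in one direction for any positive r: too few rejections, not too many.

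**The case against.** The strongest reply is that the protocol does not prescribe a wrong analysis. The AUC sentence names no test, and entering the control period as a third group is only one reading. The sample size calculation speaks of comparing, between the two arms, the change in glucose from the control period. On that reading ANCOVA has one row per participant and counts nobody twice. The same model could also report each arm's mean change with a confidence interval, which would answer legume against control. Covariates and random effects are, besides, commonly left to a statistical analysis plan, which may exist.

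Much of this stands. A reader might infer that the standard errors are definitely wrong; the text supports only that they would be if the general rule were applied with the control period as a group. A reader might also infer that Mann-Whitney and Fisher's exact test are misapplied to paired data. They are not: the first is assigned to baseline characteristics and the second to group 1 against group 2.

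What does not stand is that only detail is missing. The protocol fixes a general test, and on the change-from-control reading its arm term still addresses only the second hypothesis. Reporting and testing the mean change within each arm would repair this, but the protocol does not say so.

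**Conclusion.** The point holds in a conditional form. The control-period comparison carries the first hypothesis and is within participants, and the one rule that reaches it either ignores the pairing or, through the arm term, tests something else. If the pairing is ignored, the single-arm standard error is inflated by 1/sqrt(1 - r): about 1.2, 1.4 and 1.8 for r = 0.3, 0.5 and 0.7. With a pooled control the inflation is smaller (1.22 at r = 0.5). These sizes rest on an assumed correlation and on equal variance in the two periods.

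Two further inferences are not supported. The error does not create false positives, because it is conservative under positive correlation. It also does not touch the fermented-versus-unfermented contrast, for which ANCOVA is suitable, or the sample size of 50. Whether a real change would actually be missed depends on an effect and a correlation that nobody yet knows.

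**What to change.** In section 4, separate the two comparisons and name a method for each.

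- **Control against intervention:** analyse within-participant change, by a paired analysis in each arm or by a linear mixed model with a participant random effect, period and arm-by-period. For skewed outcomes, use the log scale or the Wilcoxon signed-rank test.
- **Fermented against unfermented:** ANCOVA of the intervention-period value on arm, with the control-period value as covariate.

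This costs a few sentences. It needs no further participants or measurements, the models are standard in R, which the protocol already names as an example, and it can be done before inclusion starts in September 2026. The paired analysis corrects the standard error only. Because the control period always comes first, it cannot separate the effect of diet from that of time.

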Fasting hemoglobin A1c (HbA1c) monitoring will be conducted at baseline, 14 days, and at day 28 by a finger prick test using a QuickRead go PLUS Instrument (#154580-4).

Systolic and diastolic blood pressures

Systolic and diastolic blood pressures will be measured at baseline, day 14, and at day 28. Blood pressures will be measured in millimeters of mercury using an automatic blood pressure monitor (Digital Automatic Blood Pressure Monitor, Omron). Participants will be asked to lie down and relax for approximately 8 to 10 minutes, and 3 blood pressure measurements will be recorded at 5-minute intervals.

Anthropometric measurements

Anthropometric measurements, such as body weight, height, waist, and hip circumference, will be measured by trained clinical dietitian students at baseline, day 14, and at day 28.

Weight, total fat mass (FM) (kg), fat-free mass (FFM) (kg), and percent body fat (%) will be measured using a calibrated Body Impedance Analytics (BIA) (TANITA MC 780 MA S, Japan).

Height (m) will be measured using a standard dynamometer without shoes and is recorded to the nearest 0.1 cm.

Body mass index (BMI) is calculated by dividing weight (kg) by height (m) squared (kg/m^2). BMI is categorized following WHO and ESPEN guidelines: underweight: $\text{BMI} < 18.5 \text{ kg/m}^2$; normal weight: $\text{BMI} 18.5 \text{ kg/m}^2 < 24.9 \text{ kg/m}^2$; overweight: $\text{BMI} 25 \text{ kg/m}^2 < 29.9 \text{ kg/m}^2$; and obesity: $\text{BMI} > 30 \text{ kg/m}^2$ (31,32).

Waist and hip circumferences will be measured using a standardized tape measure that is calibrated before use. Waist circumference (cm) will be measured at the midpoint between the lowest rib and the upper part of the iliac bone in a standing position. Hip circumference (cm) will be measured at the site of the largest circumference between the waist and thighs.

Fecal samples

Fecal samples (approximately 10 g) will be collected from all participants at baseline, day 14, and at day 28. Participants are collecting the samples by themselves using the EasySampler tool kit,

SJ-1132-120770, Version 3, 16-02-2026

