including a thorough written introduction(33,34). Fecal pH will be determined by mixing fecal matter 1:2 with sterile MilliQ-water after which pH is measured. Total fecal DNA will be extracted using standard methods. The gut microbial metagenome will be determined by shotgun high-throughput sequencing using long-read Oxford Nanopore-based sequencing(33,34). Before any further bioinformatics processing the raw reads will be purged of any human DNA-related sequences.. Fecal short chain fatty acids (SCFA) and other fecal metabolite concentrations, incl. free amino acids, are determined using high-field nuclear magnetic resonance NMR (34) on fecal samples..

Dietary intake

Data on dietary intake will be collected by three-day dietary records with photos to evaluate adherence to the intervention. The dietary records will be collected once during the control period and once during the intervention period. Photos will be used for main meals and leftovers of legumes.

Physical activity will also be documented as part of the dietary records and used to estimate energy expenditure. Furthermore, data on dietary intake will be used to assess compliance with the intervention.

Digestive abnormalities

Digestive abnormalities are identified through IBS symptoms and will be assessed using self-reported questionnaires at baseline, follow-up 1, and 2, using the IBS Severity Scoring System (IBS-SSS) for assessment of the following symptoms: abdominal distension, abdominal pain, satisfaction with bowel habits, and the extent to which symptoms affect the quality of life (QoL) (35).

Overall data collection

Table 1: Data collection

Variables	Methods	Baseline Day 0	Follow-up 1 Day 14	Follow-up 2 Day 28
Age		x		
Sex		x		
Bio markers				
Blood glucose	Continuous blood glucose levels by glucometer: Abbott Freestyle Libre PRO	x	x	x
Cholesterol levels	Prick-test	x	x	x
C-reactive protein	Prick test	x	x	x
Long-term blood glucose	Prick test	x	x	x
Blood pressure	Systolic and diastolic blood pressures	x	x	x
Body composition				
Body composition incl. body weight, kg	Body Impedance Analytics (BIA)	x	x	x
Fat mass (FM), kg		x	x	x
Fat free mass (FFM), kg		x	x	x
Height, meters	Dynamometer	x		
Body Mass Index (BMI)	BMI is calculated by dividing weight (kg) by height (m) squared (kg/m ²).	x	x	x

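### Stool DNA is sampled while the fermented arm is still eating LAB-fermented food and only human reads are removed, so ingested starter DNA can produce taxon-level, presence-based and LAB-correlation signals in that arm

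*Protocol*

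**What the plan says.** **Hypothesis.** Section 2 of the protocol expects fermented or unfermented legumes to "change gut microbiome composition, and increase SCFAs in adults, compared to a control period consuming a habitual diet". The hypothesis that compares the two arms directly concerns body composition.

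**Exposure.** Under Study design in section 3, "The second intervention period lasts from day 14 to day 28", and participants are to "consume 100 g of either fermented or unfermented legumes every day, seven days a week, for two weeks". The Intervention period text gives hummus and pasta made with legume flour as examples of the foods. It does not say which starter strains are used, at what count, or whether they are alive when eaten.

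**Sampling and laboratory work.** "Fecal samples (approximately 10 g) will be collected from all participants at baseline, day 14, and at day 28". "Total fecal DNA will be extracted using standard methods". One removal step by origin is described: "Before any further bioinformatics processing the raw reads will be purged of any human DNA-related sequences".

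**Analysis.** Section 4 lists demultiplexing, quality filtering, definition of sequence variants and taxonomy. Then "the effects of the intervention on alpha- and beta-diversity metrics, compositional changes, and correlations with anthropometrics, metabolites, and intervention arm will be evaluated", by reference to earlier publications.

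**Method conflict.** The Fecal samples text describes shotgun sequencing of the metagenome. Table 1 and section 4 describe near-full-length 16S amplicon sequencing.

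**The concern.** One arm eats food made with lactic acid bacteria and the other eats the unfermented counterpart, so starter DNA is an input to the measured outcome that differs by arm. Total fecal DNA does not distinguish resident, passing and dead cells. No stool is collected after intake stops, so the sampling schedule cannot separate them either.

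Three kinds of result are exposed: abundance of taxa that include the starter, measures that count presence or absence, and correlations of LAB taxa with metabolites, anthropometrics or arm. In the fermented arm each could partly show that the product was eaten. A report could then describe as an altered gut community what is, in part, a marker of intake.

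**Working it through.** **1. Timing and processing.** Intake runs from day 14 to day 28 without a break. Stool is taken on days 0, 14 and 28. Day 28 is therefore the only sample under intervention, and it falls within exposure. Human reads are the only ones the protocol removes by origin.

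**2. Figures from the protocol.** None bears on starter DNA. The one number used is the arm size of 25. It reproduces from the glucose calculation at the midpoint SD of 10.5 mg/dL: 2 × (1.960 + 0.842)² × 10.5² / 9² = 21.4, so 22 per arm; 22 / 0.9 = 24.4, so 25 per arm and 50 in total.

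**3. Possible starter share.** These inputs are assumptions, not in the protocol: c = 10^7 to 10^9 starter cells per g of food, 100 g of fermented product a day, 130 g of stool a day, and 10^11 cells per g of stool. If all ingested cells' DNA reached the stool and cell share equalled read share:

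share = (c × 100) / (10^11 × 130)

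| c per g | Share | Total relative to resident LAB at 0.1% | At 0.01% |
|---|---|---|---|
| 10^7 | 0.0077% | 1.08-fold | 1.8-fold |
| 10^8 | 0.077% | 1.8-fold | 8.7-fold |
| 10^9 | 0.77% | 8.7-fold | 78-fold |

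The last two columns are (resident + starter) / resident. The resident levels are also assumptions. Full recovery of DNA makes each share an upper limit for its c.

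**4. Which measures respond.** The simulation drew resident communities from one distribution in both arms and added starter reads to the fermented arm only. Assumptions: 25 per arm, 200 resident taxa, 20,000 reads per sample, one starter sequence absent from residents, starter share varying between people around a mean f, PERMANOVA with 199 permutations, and 100 runs. The table gives the percentage of runs with p at or below 0.05.

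| f | Starter taxon (Mann-Whitney) | Jaccard | Aitchison | Bray-Curtis |
|---|---|---|---|---|
| 0 | 0 | 4 | 8 | 7 |
| 0.01% | 100 | 70 | 4 | 6 |
| 0.1% | 100 | 100 | 49 | 7 |
| 1% | 100 | 100 | 100 | 23 |
| 3% | 100 | 100 | 100 | 90 |
| 10% | 100 | 100 | 100 | 100 |

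Monte Carlo error near the nominal level is about √(0.05 × 0.95 / 100) = 2.2 points. The row f = 0 is also what masking the starter and renormalising gives here.

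**5. Direct formulas.** If the resident community p is unchanged and a fraction f of reads is starter, the within-person Bray-Curtis shift is ½[Σ|p − (1 − f)p| + f] = ½(f + f) = f. A share of 0.1% thus moves a person by 0.001. In the example community Shannon changes by +0.005 at 0.1%, +0.023 at 1%, +0.036 at 3%, −0.003 at 10% and −0.157 at 20%. Richness rises by the number of starter sequences detected; whether that would reach significance was not simulated.

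**6. Simple detection.** By Fisher's exact test, starter found in 6 of 25 against 0 of 25 gives p = 0.022. With 22 per arm (25 × 0.9 = 22.5, rounded down), 5 against 0 gives p = 0.048.

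**The case against.** **A sequence filter belongs in the analysis plan.** That plan is not shown, and section 4 defers to earlier publications. This has weight: an analysis plan could add the step. But the protocol itself names the DNA template, the one removal by origin and the inferences to be drawn, and followed as written these count starter DNA as part of the effect. No later plan can change the fact that the only sample under intervention is taken during intake.

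**The protocol never says resident microbiota.** Correct. Sections 2 and 6 speak of gut microbial composition, and food-borne bacteria may legitimately count as part of what a fermented food does. This is why the result should be described accurately, not discarded.

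**The magnitude is assumed.** Also correct. The assumed load spans 100-fold, at its low end the effect is negligible on any abundance measure, and heat-treated foods may carry fewer live cells, although DNA from dead cells can still be sequenced. The simulation used a starter absent from residents. Resident LAB with the same sequence, or other fermented foods in the habitual diet (not excluded), would weaken the signal.

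**Stronger readings that the protocol does not support.** A reader might infer that diversity in general would be distorted. Within the assumed range of up to 0.77%, Bray-Curtis and Shannon hardly move, and at a high enough share Shannon falls. A reader might infer that a rise in lactic acid bacteria is set to count as support for the hypothesis. No such decision rule is written, and the microbiome hypothesis is against the control period. A reader might call the association with arm circular. It is the treatment contrast; the difficulty is only what its LAB component means.

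**Conclusion.** The point holds for a limited set of results: taxon-level findings on lactic acid bacteria, presence-based measures and LAB correlations, in the fermented arm and in the contrast between arms. The timing, the DNA template and the single removal step are all in the protocol. The size cannot be fixed from it. On the stated assumptions, a starter share of 0.01% to 0.1% of reads is enough for the taxon test and usually for Jaccard, whereas Bray-Curtis and Shannon are little affected below about 1%.

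The unfermented arm's change from the control period is unaffected, and fecal SCFA and pH are separate readouts that starter DNA does not inflate. The outcome is secondary. This is a cheap improvement to the interpretation, not a flaw that invalidates the trial. Nor does the evidence support resting every claim on masked data alone, because that would also delete true engraftment of the starter.

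**What to change.** Add to section 4 of the protocol:

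- Sequences matching the known starter strains are flagged.
- Diversity, differential abundance and correlation analyses are run both with and without the flagged sequences, renormalising after removal.
- A change beyond the ingested starter is claimed only if it persists without those sequences. Otherwise the result is described as a change in fecal composition that includes the ingested starter.
- Starter abundance is reported separately as an exposure marker.

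Reconcile the Fecal samples text (shotgun) with Table 1 and section 4 (16S). The choice determines how well starter and resident strains can be separated; strain-level separation is more feasible with shotgun data.

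**Cost.** One filter step and a second run of the same analyses. The starter identity must be recorded. Sequencing a sample of each test food would sharpen the match at the price of a few libraries, but the samples have to be kept when the food is produced, and inclusion starts in September 2026. No visit or participant burden is added.

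**Downside.** Masking also removes resident or engrafted strains that cannot be told apart from the starter, which is why both analyses are shown.
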